## 9.2. Setting

### 9.2.1. Inclusion Criteria

- Patients must meet all of the following inclusion criteria to be eligible for inclusion in the study: Age 18 years and older
- Patients with a diagnosis of COVID-19 whose information can be extracted from the I-Seha database

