### 9.2.2. Exclusion Criteria

**There are no exclusion criteria for this study.**

## 9.3 Variables

The following variables are used to obtain comprehensive descriptive results.

1. Demographics
2. Date of symptoms
3. Viral variant analysis where available (type of viral variant ie, omicron, delta etc.)
4. PCR date along with CT Value

5. Co-morbidities and
6. BMI if  $\geq 30$
7. Symptoms at presentation
8. COVID 19 vaccine status (NB 92% of population has been vaccinated -with at least one dose of COVID 19 vaccine- in Bahrain)
9. Hospital admission
10. Follow up looking at compliance and reason of non-compliance
11. Day 5,7, 21 and 28 symptoms for COVID-19 patients who receive and HRU limited to admission (ICU, ward, need for oxygen therapy) or death
12. Date of symptoms resolution if applicable

**Table 2** Table 2 below depicts the patient demographics that will be accessed during the baseline and follow-up periods. The baseline period is defined as one year before the index date. Comorbidities (full list in [Table 6](#)) and maintenance medication usage for chronic conditions (eg, statins, antihypertensives, etc.) will be described during the baseline period and follow-up periods and are listed in [Table 3](#).

Risk factors for severe COVID-19, intensive care unit (ICU) usage, invasive mechanical ventilation (IMV) usage, supplemental oxygen use, non-invasive ventilation, and high-flow nasal cannula usage are depicted in [Table 5](#) and will be extracted from the *I-Seha* national electronic health record database.

Where applicable, emerging treatment patterns may be assessed as the time from symptom onset to COVID-19 diagnosis, time from symptom onset to treatment initiation, and the time from COVID-19 diagnosis to treatment initiation as illustrated in [Table 5](#).

10Nov23 WHO recommendations for Paxlovid treatments to define: 1. COVID-19 patients who meet the WHO criteria for “strongly recommended” 2. COVID-19 patients who meet the WHO criteria for “conditionally recommended”, and 3. COVID patients who are not falling into categories 1 or 2 will be used.

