**Table 5. COVID-19 Disease Outcome Variables**

Variable	Operational definition
ICU Admission	Patients with ICU admission during COVID-related hospitalizations in the baseline and follow-up periods (excluding within 24 hours of Paxlovid™ initiation).
IMV Usage	Distribution of patients with IMV (ie, intubation and mechanical ventilation) usage, including extracorporeal membrane oxygenation (ECMO), during COVID-related hospitalizations in the baseline and follow-up periods (excluding within 24 hours of Paxlovid™ initiation).
Supplemental Oxygen Usage	Distribution of patients with supplemental oxygen usage during COVID-related hospitalizations in the baseline and follow-up periods (excluding within 24 hours of Paxlovid™ initiation).
Non-invasive Ventilation Usage	Distribution of patients with non-invasive ventilation usage during COVID-related hospitalizations in the baseline and follow-up periods (excluding within 24 hours of Paxlovid™ initiation).
High-flow Nasal Cannula Usage	Distribution of patients with high-flow nasal cannula usage during COVID-related hospitalizations in the baseline and follow-up periods (excluding within 24 hours of Paxlovid™ initiation).
Hospital Discharge Status	Distribution of patient discharge status for COVID-related hospitalizations during the baseline and follow-up periods (excluding within 24 hours of Paxlovid™ initiation). Discharge status should include transfer to skilled nursing facility, transfer to another healthcare facility, home, expired (dead), transfer to other long-term care facility, transfer to hospice based on the values recorded in the database.
Time from COVID-19 Test to Paxlovid™ Treatment	Time from the earliest COVID-19 test in the baseline period to the earliest date of Paxlovid™ prescription written date AND dispense date.
COVID-19 Lab Tests with Positive Result	The count and percentage of patients with a COVID-19 lab test with a positive result during the baseline and follow-up periods will be reported.
COVID-19 Lab Test with Variant Type	When available, the count and percentage of patients with each COVID-19 variant of concern (VOC) during the baseline period will be reported.
Monoclonal Antibody Usage	Patients with monoclonal antibody usage during the baseline and follow-up periods. Monoclonal antibody usage will include tocilizumab and bamlanivimab/etesevimab.

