### **Study population**

Patients will be eligible for inclusion in the study if they were diagnosed with COVID-19 between February and November 2022, were treated in an outpatient setting in the Kingdom of Bahrain, and were offered Paxlovid. Paxlovid was offered to patients in the Kingdom of Bahrain if they were at high risk of complications from COVID-19 due to age  $\geq$  50 years, BMI  $\geq$  35, or a medical history of chronic kidney disease (eGFR  $\geq$ 30 ml/min), diabetes mellitus, primary or secondary immunosuppressive disease or receiving immunosuppressive treatment, cardiovascular disease or hypertension, chronic lung diseases, sickle cell disease, neurodevelopmental disorders, or having a medical-related technological dependence. There are no exclusion criteria.

EHRs from approximately 3000 COVID-19 patients who were treated with Paxlovid, all of whom gave verbal consent for treatment that was recorded in the medical record, will be included in the study. These patients were treated between February and November 2022, and consist of approximately 53% of the total eligible patient population from the timeframe. A comparison group of patients will also be included. This group will consist of approximately 1000 patients with COVID-19 that were offered Paxlovid therapy but who refused treatment, over this same time period.

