**Table 1: Patient Demographic Variables**

Variable	Operational definition
Group	Received Paxlovid or did not receive Paxlovid
Age	Age will be defined as of the date of COVID-19 diagnosis using a PCR test and will be used to assign patients to age groups: 18-29, 30-49, 50-64, 65-74, $\geq 75$ years and unknown/missing age
Sex	Female, male and unknown/missing sex patients
Nationality	Nationality of the patient (Bahrain, other Middle East and North Africa, India, Pakistan, South East Asia, Caucasian)
Enrollment Date Place of Service (POS)	Type of outpatient encounter during the enrollment date (e.g., office visit, emergency room (ER), outpatient hospital, other, etc.)
Enrollment Date	Date (defined as MM/YYYY) of the enrollment date specified
Specialty of Provider at enrollment Date	Provider specialties present during the enrollment date. Patients with no provider specialty recorded will be included in an “Unknown/missing specialty” category
COVID-19 Symptom Onset Date	Date of symptom onset prior to presentation to healthcare facility

PFIZER CONFIDENTIAL

CT24-WI-GL03-RF03 2.0 *Non-Interventional Statistical Analysis Plan For Secondary Data Collection*  
*Study 01-Jun-2020*  
 Page 8 of 22

Time to COVID-19 Symptom Resolution	Time from onset of COVID-19 symptoms to resolution of symptoms
Date of COVID-19 Vaccination	Date of each COVID-19 vaccination received. Note: patient-specific vaccination history may require more than 6-months pre-index time period.
Date of Paxlovid prescription written and/or fill history (e.g., prescription claim)	Date of Paxlovid prescription written or fill history. Note: if both dates are available within the database, use the most recent date provided.

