Non-invasive Ventilation Usage	Non-invasive ventilation usage during COVID-related hospitalizations in the baseline and follow-up periods (excluding within 24 hours of Paxlovid initiation)
High-flow Nasal Cannula Usage	High-flow nasal cannula usage during COVID-related hospitalizations in the baseline and follow-up periods (excluding within 24 hours of Paxlovid initiation)
Hospital Discharge Status	Patient discharge status for COVID-related hospitalizations during the baseline and follow-up periods (excluding within 24 hours of Paxlovid initiation)

PFIZER CONFIDENTIAL

CT24-WI-GL03-RF03 2.0 *Non-Interventional Statistical Analysis Plan For Secondary Data Collection*  
*Study 01-Jun-2020*  
 Page 11 of 22

Time from COVID-19 Test to Paxlovid Treatment	Time from the earliest COVID-19 test in the baseline period to the earliest date of Paxlovid prescription written date AND dispense date.
COVID-19 Lab Tests with Positive Result	COVID-19 lab test with a positive result during the baseline and follow-up periods.
COVID-19 Lab Test with Variant Type	When available, COVID-19 variant of concern (VOC) during the baseline period.
Treatment drugs being receiving at the index date	-Use Positive test as the INDEX Date and record use of any medicine listed in the potential DDI/Contraindications section of the EUA/:Label
Monoclonal Antibody Usage	Monoclonal antibody usage during the baseline and follow-up periods. Monoclonal antibody usage will include tocilizumab and bamlanivimab/etesevimab. (Yes/No)
Antiviral Usage	Antiviral therapy usage during the baseline and follow-up periods. Antiviral therapy usage will include remdesivir, nirmatrelvir/ritonavir (paxlovid) and molnupravir. (Yes/No)
Steroid therapy	Steroid therapy during admission (Yes/No)

PFIZER CONFIDENTIAL

CT24-WI-GL03-RF03 2.0 *Non-Interventional Statistical Analysis Plan For Secondary Data Collection*  
*Study 01-Jun-2020*  
 Page 12 of 22

WHO guidelines on COVID-19 therapeutics include the following groups

- **High risk:** people who are immunosuppressed; estimated hospitalization rate of 6%.
- **Moderate risk:** >65 years of age, conditions like obesity, diabetes and/or chronic conditions including chronic obstructive pulmonary disease, kidney or liver disease, cancer, with disabilities, and with comorbidities of chronic disease; estimated hospitalization rate of 3%.
- **Low risk:** those who are not in the high or moderate risk categories; low risk of hospitalization (0.5%) – most people are low risk.

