**LIST OF TABLES AND TABLE SHELLS****Table 3: Descriptive statistics for baseline variables**

Variables	Group		P-value	Effect size
	Paxlovid	Control		
Age, % (n)				
18-29				
30-49				
50-64				
65-74				
≥75 years				
Gender, % (n)				
Male				
Female				
Nationality, % (n)				
Bahrain				
Other Middle East and North Africa				
India				
Pakistan				
South East Asia				
Caucasian				

PFIZER CONFIDENTIAL

CT24-WI-GL03-RF03 2.0 *Non-Interventional Statistical Analysis Plan For Secondary Data Collection Study* 01-Jun-2020  
 Page 16 of 22

Enrollment Date Place of Service (POS), % (n)				
Office visit				
Emergency room				
Outpatient hospital				
Other				
Specialty of Provider at enrollment Date				
Interns				
Residents				
Family Phyiscans				
Specialist				
Consultants				
Number of days from COVID-19 symptom onset to resolution, mean (SD)				
Number of days from vaccination to contracting COVID-19, mean (SD)				
Number of days from contracting COVID-19 to being prescribed Paxlovid, mean (SD)				
Number of days from COVID-19 test to Paxlovid treatment, mean (SD)				
COVID-19 Lab Tests with Positive Result, % (n)				
COVID-19 Lab Test with Variant Type, % (n)				

PFIZER CONFIDENTIAL

CT24-WI-GL03-RF03 2.0 *Non-Interventional Statistical Analysis Plan For Secondary Data Collection Study* 01-Jun-2020  
 Page 17 of 22

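### Two laboratory rows in the SAP baseline table need redefining: the positive-test row is at or near 100% and hides earlier infection, and the variant row's window is anchored differently in the two groups

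*SAP*

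**What the plan says.** **Positive-test row.** SAP Table 4 defines it as "COVID-19 lab test with a positive result during the baseline and follow-up periods". Protocol Table 5 uses the same window and makes it a patient-level summary: "The count and percentage of patients with a COVID-19 lab test with a positive result during the baseline and follow-up periods will be reported". The SAP's Table 3 shell, headed as baseline variables, lists the row with P-value and effect-size columns.

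**Variant row.** SAP Table 4: "When available, COVID-19 variant of concern (VOC) during the baseline period". It appears in the same baseline shell.

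**Windows.** The SAP does not define the baseline period. Protocol section 9.3 does: "The baseline period is defined as one year before the index date". Protocol Table 1 sets the index date as the diagnosis date for controls. For treated patients it is the prescription or dispense date, the more recent if both exist, with the diagnosis date as fallback if neither does. In SAP Table 4, the row on medicines in use at index instead anchors index on the positive test.

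**Entry.** Protocol section 9.2.1 asks for "Patients with a diagnosis of COVID-19 whose information can be extracted from the I-Seha database". The SAP's study population covers patients who "were diagnosed with COVID-19 between February and November 2022". PCR is tied to diagnosis only in the age definition of SAP Table 1: "Age will be defined as of the date of COVID-19 diagnosis using a PCR test".

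**Prior infection.** Earlier SARS-CoV-2 infection appears in no variable table of either document, and not in the SAP's list of propensity-score characteristics.

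**The concern.** A baseline row should describe patients before, or at, the point where the groups are compared, and in the same way in both groups. Neither row does this.

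The positive-test row mixes the test that brought the patient into the study with earlier and repeat positives, and adds follow-up results to a baseline table. The comparison therefore carries almost no information, although the same search of the baseline year could show documented prior infection, a plausible prognostic factor.

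The variant row uses a window whose end point differs by group. For a treated patient it can hold the current infection; for a control it may hold only earlier ones. Protocol Table 1 relies on both cohorts falling in the same dominant-variant era, and this row is the only tabulated result that would let a reader check that. A difference produced by the window could be mistaken for a difference in circulating variant or in testing.

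**Working it through.** The documents give no expected rate or sample-size figure for these rows, so there is nothing to reproduce. I traced the definitions and applied the SAP's own tests to the approximate group sizes in its study population section, 3000 treated and 1000 controls.

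**1. Positive-test row.** If every patient's diagnostic test is on record and inside the pooled window, the table is 3000/3000 versus 1000/1000. The difference is 0. Chi-square cannot be computed because an expected count is zero. Fisher's test gives p = 1 with an undefined odds ratio. Cramer's V is 0/0. These results are the same whatever share of patients had an earlier infection.

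If day 0 belonged to neither period, a control would count only through another positive test. Assume 5-20% of controls have one and every treated patient's test predates index. The row then reads 100% versus 5-20%, with V from 0.97 to 0.87: a pure window artefact.

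**2. Variant row: where the index-infection result falls.** This takes the protocol's wording literally, with day 0 outside baseline.

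| Patient | Index date | Result dated | In baseline? |
|---|---|---|---|
| Control | Diagnosis | Diagnosis day | No |
| Control | Diagnosis | Day before diagnosis | Yes |
| Treated | Prescription or dispense | Before index | Yes |
| Treated | Same day as test, or fallback to diagnosis | Index day | No |

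**3. Variant row: size.** Three inputs are assumed because the documents give none:
- s, the share of infections with a variant result, equal in both groups: 5-50%
- q, the share of treated patients indexed on the test day: 0-90%
- r, the share with an infection in the prior year, equal in both groups: 5-20%

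Controls are taken as dated on the diagnosis day. The expected row values are:

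- Controls: r × s
- Treated: (1 − q) × [1 − (1 − s)(1 − r × s)] + q × r × s

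For s = 0.20, q = 0.25, r = 0.05: controls 0.05 × 0.20 = 0.010; treated 0.75 × [1 − 0.80 × 0.99] + 0.25 × 0.010 = 0.156 + 0.0025 = 0.1585.

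| s | q | r | Treated | Control | Chi-square p | V |
|---|---|---|---|---|---|---|
| 5% | 90% | 5% | 0.7% | 0.3% | 0.13 | 0.02 |
| 5% | 90% | 20% | 1.5% | 1.0% | 0.24 | 0.02 |
| 5% | 50% | 20% | 3.5% | 1.0% | 0.00005 | 0.06 |
| 20% | 90% | 20% | 5.9% | 4.0% | 0.02 | 0.04 |
| 20% | 25% | 5% | 15.8% | 1.0% | < 0.0001 | 0.20 |
| 50% | 0% | 5% | 51.2% | 2.5% | < 0.0001 | 0.43 |

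True typing and prior infection are equal in the two groups in every line, so each gap comes from the window alone.

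**4. Prior infection: illustration only.** Suppose prevalence is 20% treated versus 30% control, and prior infection multiplies the risk of hospital use by k. With no treatment effect, the unadjusted risk ratio is (0.2k + 0.8)/(0.3k + 0.7): 0.86/0.79 = 1.089 at k = 0.3 and 0.90/0.85 = 1.059 at k = 0.5, a shift of 6-9%. None of these inputs is in the documents.

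**The case against.** **Entry does not guarantee 100%.** A reader might infer that every patient must have a positive test by the entry rule. The documents do not say so: entry needs a diagnosis, PCR is named only in the age definition, and variables are extracted if available. This stands. The row may fall below 100%, but the shortfall would then describe record completeness.

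**A P-value can be produced.** A reader might infer that the planned comparison cannot be run. The SAP allows Fisher's test where appropriate, and it returns p = 1. This also stands: the result exists but tells the reader nothing.

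**The index rules are not settled.** Neither document says which period holds day 0, or whether diagnosis is dated by sample or by result. The positive-test anchor in SAP Table 4, if applied to every row, would treat the groups alike. That removes the asymmetry, but both groups could then lose their own variant result.

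**Same-day prescribing may be common.** The clinic aimed to treat as early as possible. A reader might infer that controls would show essentially no variant results against a highly significant treated count. That needs no same-day prescribing and no typed earlier infections in controls, which the documents do not support. With mostly same-day prescribing and little typing, the gap is negligible.

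**Little depends on these rows.** The common era is set by the identification period, the variant row feeds no model, and the protocol's variable list collects variant without a window, so no data are lost. All of this is fair. It limits the consequence to misleading table rows, and makes the repair easy.

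**Prior infection is an added covariate.** True, and the study is called descriptive. But the SAP plans inferential comparisons and propensity matching, and the row already searches the tests that would show it.

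**Conclusion.** Both rows should be redefined before programming. They are secondary descriptive rows, not primary results.

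The positive-test row is uninformative on any reading: at or near 100% in both groups, a measure of record completeness if lower, or a window artefact if day 0 lies in neither period. It cannot separate earlier infection from the index infection.

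The variant row, read literally, omits a control's result dated on the diagnosis day and includes a treated patient's result dated before the prescription. Over the ranges checked, the artefact runs from 0.7% versus 0.3% (p = 0.13) to 51.2% versus 2.5%. Where it lies depends on four facts the documents do not state: the period that holds day 0, sample or result dating, the share of treated patients indexed on the test day, and the typing rate.

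The 6-9% risk-ratio shift shows only how prior infection could matter. It is not an estimate for this study.

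**What to change.** 1. Define variant type as the result from the index diagnostic specimen in both cohorts, tabulated by variant with a not-typed category.
2. State which period contains day 0 and whether diagnosis is dated by sample or result. Say whether the positive-test anchor applies only to the medication row.
3. Replace the positive-test row with documented prior SARS-CoV-2 infection: a positive test in the baseline year from an earlier episode, separated from the index PCR by a gap fixed in advance.
4. Report repeat positives after day 0 separately, outside the baseline table.
5. Add prior infection to the propensity list where available.

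The cost is two definitions and their shell rows; the present rows already call for test results over the baseline year. The limitation is that prior infection will be under-recorded, since only tests on record count, and the report should say so.

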Antiviral Usage	Patients with antiviral therapy usage during the baseline and follow-up periods. Antiviral therapy usage will include remdesivir, nirmatrelvir/ritonavir (Paxlovid™) and molnupiravir.
Steroid therapy	Patients with steroid therapy during admission

PFIZER CONFIDENTIAL

CT24-WI-GL02-RF02 4.0 Non-Interventional Study Protocol Template For Secondary Data Collection Study

15-Jun-2022

Page 19 of 41

Variable	Operational definition
Treatment drugs being receiving at the Index date	Use Positive test as the INDEX Date and record use of any medicine listed in the potential DDI/Contraindications section of the EUA/Label

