**Table 7. Potentially Significant Drug Interactions**

Drug Class	Product name
Antiangular	RANOLAZINE
Antiarrhythmics	BEPRIDIL
	LIDOCAINE (SYSTEMIC)
Anticancer agents	ABEMACICLIB
	CERITINIB
	DASATINIB
	ENCORAFENIB
	IBRUTINIB
	IVOSIDENIB
	NERATINIB
	NILOTINIB
	VENETOCLAX
	VINBLASTINE
	VINCRISTINE
Anticoagulants	WARFARIN
	RIVAROXABAN
Antidepressants	BUPROPION
	TRAZODONE
Antifungals	KETOCONAZOLE
	VORICONAZOLE
	ISAVUCONAZONIUM SULFATE
	ITRACONAZOLE
Anti-HIV protease inhibitors	AMPRENAVIR
	ATAZANAVIR
	DARUNAVIR
	FOSAMPRENAVIR
	INDINAVIR
	NELFINAVIR

PFIZER CONFIDENTIAL

CT24-WI-GL02-RF02 4.0 Non-Interventional Study Protocol Template For Secondary Data Collection Study

15-Jun-2022

Page 33 of 41

Drug Class	Product name
	SAQUINAVIR
	TIPRANAVIR
Anti-HIV	DIDANOSINE
	DELAVIRDINE
	EFAVIRENZ
	MARAVIROC
	NEVIRAPINE
	RALTEGRAVIR
	ZIDOVUDINE
Anti-infective	CLARITHROMYCIN
	ERYTHROMYCIN
Antimycobacterial	BEDAQUILINE
	RIFABUTIN
Antipsychotics	QUETIAPINE
Calcium channel blockers	AMLODIPINE
	DILTIAZEM
	FELODIPINE
	NICARDIPINE
	NIFEDIPINE
Cardiac glycosides	DIGOXIN
Endothelin receptor antagonists	BOSENTAN
Hepatitis C direct acting antivirals	ELBASVIR/GRAZOPREVIR
	GLECAPREVIR/PIBRENTASVIR
	SOFOSBUVIR/VELPATASVIR/VOXILAPREVIR
	OMBITASVIR/PARITAPREVIR/RITONAVIR AND DASABUVIR
HMG-CoA reductase inhibitors	ATORVASTATIN
	ROSUVASTATIN
Hormonal contraceptive	ETHINYLMESTRADIOL

Drug Class	Product name
Immunosuppressants	CYCLOSPORINE
	TACROLIMUS
	SIROLIMUS
Long-acting betaadrenoceptor agonist	SALMETEROL
Narcotic analgesics	FENTANYL
	METHADONE
Sedative/hypnotics	MIDAZOLAM (ADMINISTERED PARENTERALLY)
Systemic corticosteroids	BETAMETHASONE
	BUDESONIDE
	CICLESONIDE
	DEXAMETHASONE
	FLUTICASONE
	METHYLPREDNISOLONE
	MOMETASONE
	PREDNISONE
	TRIAMCINOLONE

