1.0 Demographics			
1.1 Age	-		
1.2 Gender	-		
2.0 Clinical Characteristics	-		
2.1 Comorbidities (ICD-10)	-		
2.2 Vaccination Status (incl. date)	-		
2.3 Baseline Medication Usage	-		
2.4 COVID-19 Symptom (incl. date)	-		
2.5 COVID Diagnosis Date (index)	-		
Outcome Variables	-		
3.0 HRU	-		
3.1 Hospitalizations	-		
3.2 Outpatient Visits	-		
3.3 Emergency Room Visits	-		
3.4 Procedures	-		
3.5 Laboratory Tests (incl. COVID-Related)	-		
4.0 Medical Costs (incl. COVID-Related)	-		
4.1 Outpatient Costs	-		
4.2 Inpatient Costs	-		
4.3 Emergency Room Costs	-		
4.4 Ancillary Costs	-		
5.0 Pharmacy Costs (incl. COVID-Related)	-		

	Treated COVID-19 patients (N = n) Control Group Untreated COVID-19 patients (N = n)
6.0 Medication Usage (incl. written date of prescription and fill history)	-
6.1 Antibiotic	-
6.2 Antiviral (incl. Paxlovid™, COVID-19 monoclonal antibodies)	-
6.3 Antithrombotic	-
6.5 Anti-inflammatory (incl. steroids)	-

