**Table 7: Descriptive statistics for outcome variables**

Outcome Variables	Group		P-value	Effect size
	Paxlovid	Control		
Hospitalizations, % (n)				
Number of hospitalizations per patient, mean (SD)				
Number of hospitalizations per patient among patients with readmissions, % (n)				
Time to first outpatient encounter, mean (SD)				
ICU Admission, % (n)				
Hospital Length of Stay, mean (SD)				
ICU/Non-ICU LOS, mean (SD)				
IMV/No IMV LOS, mean (SD)				
Treatment				
IMV Usage, % (n)				
Supplemental Oxygen Usage, % (n)				
Non-invasive Ventilation Usage, % (n)				
High-flow Nasal Cannula Usage, % (n)				
Hospital Discharge Status				
Went home, % (n)				
Transfer to skilled nursing facility, % (n)				

PFIZER CONFIDENTIAL

CT24-WI-GL03-RF03 2.0 *Non-Interventional Statistical Analysis Plan For Secondary Data Collection Study* 01-Jun-2020

Page 20 of 22

Transfer to other healthcare facility, % (n)				
Transfer to other long-term care facility, % (n)				
Transfer to hospice, % (n)				
Death, % (n)				
Medication Usage, % (n)				
Antibiotic, % (n)				
Antiviral (incl. Paxlovid, COVID-19 monoclonal antibodies), % (n)				
Antithrombotic, % (n)				
Anti-inflammatory (incl. steroids), % (n)				

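### Interacting drugs at index and baseline maintenance medication have no SAP results row and no place in the propensity factors, and SAP Table 7 does not separate existing from new drug use

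*SAP*

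**What the plan says.** **Collection.** Protocol Table 5 and SAP Table 4 both define a variable for potentially interacting or contraindicated medicines, anchored to the positive test. The SAP instruction is to "record use of any medicine listed in the potential DDI/Contraindications section" of the EUA or label. The protocol wording is "Use Positive test as the INDEX Date and record use of any medicine listed in the potential DDI/Contraindications section of the EUA/Label". Protocol Table 7, titled "Potentially Significant Drug Interactions", lists products by class. Both documents place the variable among disease outcomes.

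**Promise to describe.** Protocol 9.3 says that "maintenance medication usage for chronic conditions (eg, statins, antihypertensives, etc.) will be described during the baseline period and follow-up periods". It points to protocol Table 3 for the list, but that table has no medication row. The sample results table (protocol Table 8) does have one: "2.3 Baseline Medication Usage".

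**SAP results shells.** SAP Table 3, "Descriptive statistics for baseline variables", has no medication row. SAP Table 6 mentions drugs only as immunosuppressive treatment, inside a composite risk factor. SAP Table 7, the outcome shell, has four medication-use rows: antibiotic, antiviral, antithrombotic (the row beginning "Antithrombotic, % (n") and anti-inflammatory including steroids. None carries a time window. SAP Table 8 concerns the WHO and national recommendations only.

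**Adjustment.** The propensity list at the end of the SAP's inferential statistics section names eight factors: age, sex, vaccination status, high-risk status, healthcare seeking, socioeconomic factors, residence and comorbidities. None is a medication. SAP 1.11 (Covariates) is marked not applicable.

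**The concern.** The SAP compares outcomes between patients who took Paxlovid and patients who were offered it and refused. A drug that interacts with Paxlovid could plausibly affect that choice, and being on such a drug also marks underlying illness. A variable of that kind belongs in the baseline comparison and should at least be checked for balance after matching. As drafted, it is extracted, treated as an outcome and given no row.

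SAP Table 7 adds a second problem. The protocol's sample table lists antithrombotic and anti-inflammatory use as outcomes, but alongside a baseline medication row. The SAP keeps the outcome rows and drops the baseline row. Protocol Table 7 lists warfarin, rivaroxaban and systemic corticosteroids, so the overlap is direct. A patient on long-term warfarin can appear in an outcome row, and a difference between groups that was present before COVID-19 would then read as a difference in outcome.

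**Working it through.** The plan gives no figure on this point, so there is none to reproduce. The check is textual, followed by an illustration.

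**1. Trace each item through the SAP.**

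| Item | SAP variable table | SAP results shell | Propensity factor |
|---|---|---|---|
| Interacting/contraindicated drug at index | Table 4 (outcomes) | none (Tables 3, 6, 7, 8) | no |
| Baseline maintenance medication | none (Tables 1, 2, 4) | none | no |
| Antithrombotic use | none | Table 7, no window | no |
| Anti-inflammatory use including steroids | Table 4 has steroids, during admission only | Table 7, no window | no |

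**2. Illustrate the confounding.** Let pT and pC be the shares on an interacting drug among treated patients and refusers, and r the ratio of admission risk in users to that in non-users. If Paxlovid has no effect, the crude risk ratio is

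RR = (1 + pT(r − 1)) / (1 + pC(r − 1)).

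The documents give none of the three inputs. Assume pT = 0.20 to 0.30, pC = 0.30 to 0.40 and r = 1.5 to 2.

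| pT | pC | r | RR with no Paxlovid effect |
|---|---|---|---|
| 0.20 | 0.40 | 2 | 1.20/1.40 = 0.857 |
| 0.20 | 0.40 | 1.5 | 1.10/1.20 = 0.917 |
| 0.20 | 0.30 | 2 | 1.20/1.30 = 0.923 |
| 0.20 | 0.30 | 1.5 | 1.10/1.15 = 0.957 |
| 0.30 | 0.40 | 2 | 1.30/1.40 = 0.929 |
| 0.30 | 0.40 | 1.5 | 1.15/1.20 = 0.958 |
| 0.30 | 0.30 | either | 1.00 |

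The range is 0.86 to 1.00. The direction is assumed too: if use were higher among the treated, for example 40% v 20% with r = 2, the ratio would be 1.40/1.20 = 1.17.

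**3. Would a row be informative?** With about 3000 treated and 1000 refusers (SAP 1.5) and use of 20% v 30%, the 95% half-width for the difference is 1.96 × √(0.2 × 0.8/3000 + 0.3 × 0.7/1000) = 0.032. A 10-point imbalance would be estimated to within about 3.2 points, so one row would largely show which line of the table applies.

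**The case against.** Several points on the other side have force.

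- **The variable is in the SAP.** It is defined in SAP Table 4, and SAP 7.2.3 promises descriptive statistics for every variable. A reader might infer that it appears nowhere, or will not be described; neither is right. What is missing is a shell row and any use in adjustment. SAP 7.2.3 does not rescue maintenance medication, which is in no SAP variable table.
- **Proxies are already listed.** Amlodipine, atorvastatin, warfarin and tacrolimus treat conditions that comorbidities and high-risk status capture. Matching on those should remove part of any imbalance, so the ratios above are not residual bias. The proxies are only partial, because two patients with the same diagnosis can differ in whether they take an interacting drug.
- **Reasons for refusal are undocumented.** It is tempting to call interacting drugs a likely driver of refusal. No passage says so, and the documents do not say whether patients on contraindicated drugs were offered Paxlovid at all.
- **The primary objective does not name medication.** Protocol Table 8 is labelled a sample, and protocol 9.7 lets the SAP modify the plan. A reader might infer that part of the primary objective has been lost; the text does not go that far. The statement in protocol 9.3 remains unmet.
- **Timing is partly covered.** SAP Table 4 limits steroid therapy to the admission, and protocol Table 8 foresees prescription and fill dates. For antithrombotics there is no limit. This is an ambiguity that permits miscounting, not proof that it will occur.
- **Adding the variable to the score can cost overlap** if it predicts refusal strongly and outcome weakly. That is a reason to allow a justified omission, but not to leave balance unreported.

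**Conclusion.** The concern holds in a limited form. An index-date variable that both documents collect is filed as an outcome, has no results row and is outside the propensity factors. Maintenance medication promised in protocol 9.3 has dropped out of the SAP altogether. Two SAP Table 7 rows can mix long-standing with new drug use.

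The size of any bias cannot be determined from the documents. The range of 0.86 to 1.00 rests on assumed prevalences and an assumed risk ratio, on higher use among refusers, and on no adjustment by the eight listed factors. If use is balanced, this source adds no bias. The case for change is that the plan, as drafted, does not commit to showing which situation applies, although the interacting-drug data are already to be extracted. It should be corrected before analysis.

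**What to change.** 1. Move the interacting-drug variable from SAP Table 4 to the baseline variables.
2. Add two rows to SAP Table 3 or Table 6: any interacting or contraindicated drug at index (yes/no), and maintenance medication. Add maintenance medication to the SAP variable list.
3. Add interacting drug at index to the propensity factors and report its balance after matching. If it is left out because it harms overlap, say so and still report balance.
4. In SAP Table 7, report antithrombotic and anti-inflammatory drugs started after index separately from those already in use at index. State the dividing date. The positive test exists in both groups and already anchors the drug variable, whereas protocol Table 1 normally indexes treated patients at prescription or dispensing.

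A breakdown by the 22 classes of protocol Table 7 is optional and should be descriptive only. With a p-value per row at 0.05 and no multiplicity adjustment, about 22 × 0.05 = 1.1 false positives would be expected if no class differed.

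**Cost:** a few rows, one more covariate, a possible small loss of overlap, and extraction of maintenance medication, which the protocol promises but the SAP does not yet list.
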